## **16 SECONDARY CLINICAL OUTCOMES**

Aspartate aminotransferase (AST) and alanine aminotransferase (ALT) are extracted from all participants electronic health records (EHRs) who had already achieved viral cure at baseline and who were not on HCV treatment at baseline in order to determine feasibility of extracting these data from the medical record

and explore pre and post intervention mean scores in these two markers of liver inflammation. Mean AST and ALT levels are compared in both females and males.

## 17 EXPLORATORY PATIENT-REPORTED OUTCOME MEASURE

**17.1 Satisfaction with Telehealth Session Mean Score.** After session 1 and session 14, participants complete a 15-item acceptability/satisfaction survey about their satisfaction with using telehealth sessions. Items are scored on a scale from 1= strongly disagree to 5=strongly agree. The average Total Telehealth Satisfaction score is analyzed from session 1 and session 10, which could range from 1 to 5 with higher scores indicating greater satisfaction.

## 18 EXPLORATORY STRESS BIOMARKER OUTCOME

Participants in both conditions collect saliva samples at baseline (T1) and post-treatment (T4). Cortisol secretions follow a diurnal pattern, but physiological and psychological stress disrupt normal rhythms, dysregulate the sympathetic nervous system and HPA axis and are associated with poor health. Conversely, stress management skills regulate cortisol patterns. Participants will be given two salivary collection kits to provide salivary samples pre- and post-intervention. Participants will provide salivary samples four times: immediately upon waking, 30 minutes after awakening, in the late afternoon, and at bedtime. Research staff will contact patients the day prior to collection to remind them of the protocol. Samples will be stored in participants' home refrigerators within 30 minutes of collection and mailed to UNC in pre-paid gel wrap mailers. Samples will be stored at  $-80^{\circ}\text{C}$  until assayed. Collection and storage methods have been validated. Saliva samples will be stored de-identified using subject ID number only. Mean  $\log_{10}$  cortisol as a diurnal function of time of day and summary values such as the area under the curve (AUC), AUC minus ground will be compared from T1 to T4. Lower cortisol levels indicate a lower level of stress.

## 19 INTERVENTION TARGETS

VC-CBCS participants will complete a weekly *Post-Intervention* Form after each of 14 sessions directly into REDCap on their iPad or home technology.

**19.1 SMART** Goals related to health changes, stress management, and cognitive-behavioral skills. After each new session, each patient will describe at least one new SMART goal related to the session topic such that after session one, they describe one goal...after session 14, they describe 14 goals, one per topic.

**19.2** For each SMART goal, patients will rate the *Importance/Relevance* of the particular goal, their *Motivation* to achieve the goal, and their *Self-Efficacy* to achieve the particular goal. The three ratings will be on a Numeric Rating Scale ranging from 0% to 100%.

## 20 PATIENT SOCIODEMOGRAPHICS

At baseline (T1), all participants will self-report the following NINR data elements: age, sex, race, ethnicity, marital status, income, education level, employment status, caregiver type, household member total count, and health comorbidities. History of psychiatric, alcohol and substance use issues will be obtained during the screening process and transferred to the research database for enrolled patients. All data will be cross-validated with data reviewed in patients' EHRs.

## 21 PROTOCOL FIDELITY

To examine the Group Facilitator's competency and fidelity to the intervention protocol and 14 modules, we will utilize two observer-rating forms to evaluate *Facilitator Adherence* and *Facilitator Competency* to manage group dynamics. A research staff member will observe VC-CBCS sessions and complete the observer-rating Facilitator Adherence form, rating the proportion of sections completed on scale of 0-100%. The staff member will also complete the Facilitator Competency observer-rating form, a 14-item Likert

scale (1=not at all; 4=extremely). The Facilitator will not have access to these ratings until completion of each cohort.

## **22 ELECTRONIC DATA CAPTURE AND SECURE STORAGE**

Data will be directly entered and stored in the web-based research electronic data capture system, REDCap (<https://projectredcap.org/>). The REDCap system is a secure, HIPAA-compliant web-based application to support distributed data collection governed by standard University, School of Medicine, and Federal information security policies and standards. The REDCap application is hosted and monitored on a secure server located within the UNC CTSA-funded NC TraCS Institute's Bioinformatics Core. Access to the REDCap database for this study will be restricted to authorized research team members as needed to perform their job functions. Research staff who access the REDCap system will use a unique user ID provided by the Bioinformatics Core. Research staff will enter EHR data into clinical forms on REDCap. Each time research staff access REDCap, a unique electronic signature (login) is required, and REDCap maintains an audit trail of all activity. Participants will be given the choice of providing PRO data (a) directly into REDCap from a weblink set up on their iPad, (b) from an automated email from the REDCap system that contains a URL link to the survey or (c) through phone-delivered surveys with study staff who enter responses directly into REDCap. Each REDCap link is unique to each subject and each assessment period. Patients will be sent electronic reminders from REDCap to approved email addresses when PRO data entry is needed.

For each consented patient, their consent documents will be uploaded and stored in REDCap. Hard copy consent documents will be stored in a secure location.

While the research data will be stored in REDCap, other study materials (e.g., SAE/AE forms, reimbursements, audio-video recordings) will be securely stored on VPN- and password protected CGIBD secure server in a study folder. The server and study folders are maintained and monitored by UNC SOM ITS. ITS will provide access only to staff working on this project. No study-related documents containing patient PHI or identifiers will reside on desktop or laptop computers.

## **23 DATA ANALYSIS**

### **23.1 Statistical Analysis Overview**

The analysis strategies are designed to inform the feasibility and planning of a subsequent efficacy RCT. No hypothesis tests will be conducted. Statistical estimates will be reported with 95% confidence intervals (CIs) or standard deviations. Collectively, the results of this preparatory study will allow us to formulate reasonable expectations for the subsequent RCT. A publicly available PROMIS® scoring system is available for computing PROMIS T-scores. Statistical computations will be performed in SAS software (SAS Institute, Cary, NC).

### **23.2 Aim 1: Feasibility of conducting a RCT**

Frequencies will be tabulated for the following: patients approached/called, consented, randomized/enrolled, retained, completed surveys, and salivary cortisol samples. We will examine reasons for refusal, causes of dropout, session attendance, causes and patterns of missing data, and technical and logistical difficulties with delivering the intervention via VC. *We anticipate that >50% of approached/called patients will consent; >75% of consented patients will be randomized and enroll; >80% will be retained; and >90% of PRO and cortisol data will be collected.*

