## **3 STUDY DESIGN**

### **3.1 Study Design**

This pilot feasibility study was designed as a preparatory two-arm small randomized controlled trial (RCT) with a total enrollment of 32 participants assigned by randomization to VC-CBCS (n=24) or SC (n=8) to address the specific aim.

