## 7 REIMBURSEMENT

Participants in both conditions will be reimbursed \$25 for four patient-reported outcomes (PROs) assessments and two days of salivary sample collection. Completion of PROs during each assessment period will take 20-30 minutes. Patients randomized to VC-CBCS will be reimbursed \$25 to participate in an exit focus group. For reimbursement of VC-CBCS sessions, participants will be reimbursed for cellular and wi-fi data plans, if needed for iPad use, and will be given two options: (1) retain the iPad (worth \$300) after the study ends; (2) receive a rechargeable Visa gift card at the beginning of the study that will be recharged with \$300 after the intervention ends and iPad is returned. Participants will check their preference for one of these two options on the consent form. Participant preferences will be tracked in a Reimbursement Log to inform reimbursement options for a future RCT.

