## 8 RANDOMIZATION

Four groups of patients will be randomized and will consist of 7-9 patients each. The groups are as follows:

- Group 1 - 7 patients with 5 randomized to VC-CBCS and 2 to SC;
- Group 2 - 9 patients with 7 randomized to VC-CBCS and 2 to SC;
- Groups 3 and 4 - 8 patients each with 6 randomized to VC-CBCS and 2 to SC each group.

Once each group meets their respective necessary number of patients, they will be randomized. We will use these randomization procedures for a total of 24 participants randomized to VC-CBCS and 8 randomized to SC and overall 3:1 ratio. A computer-based procedure for permuted-block randomization and concealment will be implemented by non-study staff. No study personnel will have access to the randomization schedule. The computer-generalized randomization scheme will automatically randomize patients who are enrolled to one of the two group assignments after each wave is enrolled. Participants will be subsequently called and informed of group assignment.

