## **13 PRIMARY FEASIBILITY OUTCOME MEASURES**

- 13.1** Percentage of Patients Consented Versus Approached
- 13.2** Percentage of Participants Consented Versus Randomized
- 13.3** Percentage of Standard of Care Condition Participants Retained vs Enrolled
- 13.4** Percentage of VC-CBCS Intervention Condition Participants Retained vs Enrolled
- 13.5** Percentage of Surveys Completed by Participants Who Completed the Study

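### Survey and saliva completeness is not reported by arm, and 13.5 counts study completers only, so with a 24:8 split the >90% figure can be met while standard-care data are poor

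*Combined protocol and SAP*

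**What the plan says.** Section 8 plans for a "total of 24 participants randomized to VC-CBCS and 8 randomized to SC and overall 3:1 ratio". Section 23.2 then gives the Aim 1 expectations in a single sentence that opens "We anticipate that >50% of approached/called patients will consent" and ends ">80% will be retained; and >90% of PRO and cortisol data will be collected". Neither of the last two figures is attached to an arm or to a stated denominator.

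The primary feasibility outcomes in section 13 treat the two quantities differently:

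- **Retention** is split. Outcome 13.3 is "Percentage of Standard of Care Condition Participants Retained vs Enrolled", and 13.4 is its VC-CBCS counterpart.
- **Survey completion** (13.5) is one percentage, not split by arm, and limited to those who completed the study.
- **Saliva completeness** is not listed in section 13. It appears only in the tabulations and the anticipated figure of 23.2.

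Both arms have the same four PRO assessments (11.1, 12.3) and the same two saliva collection days (7, 11.2, 18). VC-CBCS participants also submit self-report data after each of the 14 sessions (11.3, 19).

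**The concern.** Aim 1 asks whether a randomized comparison with standard care can be run, including whether its data can be collected. The future trial therefore needs to know how complete the data are in each arm. A pooled percentage answers mainly for VC-CBCS, which supplies 24 of the 32 participants.

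The arms also differ in ways that could affect completeness. Section 9 describes minimal staff contact with SC participants outside the assessment windows. Section 7 gives VC-CBCS alone the $25 exit-group payment and the iPad or $300 card. Lower SC capture is thus plausible, though the documents do not establish it.

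The restriction to completers in 13.5 adds a second problem. Anyone who drops out leaves the denominator, so the outcome misses the incomplete data that dropout causes. If the pilot reports capture above 90% on this basis, the efficacy trial could be planned with too little allowance for missing control-arm data.

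**Working it through.** **Inputs.** Group sizes come from section 8, the four PRO time points from 12.3, the two saliva days of four samples each from 11.2 and 18, and the anticipated figures from 23.2.

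**Allocation reproduced.** VC-CBCS: 5 + 7 + 6 + 6 = 24. SC: 2 × 4 = 8. Total 32, ratio 3:1, as stated. The 80% and 90% figures have no derivation in the documents to reproduce.

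**Data capture, all randomized.** The smallest whole count strictly above 90% of the pooled total, minus complete VC-CBCS data, gives the lowest SC count that still meets the figure.

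| Measure | Pooled total (VC-CBCS + SC) | Count needed | Lowest SC count if VC-CBCS complete |
|---|---|---|---|
| PRO assessments | 96 + 32 = 128 | 116 (90.6%) | 116 − 96 = 20 of 32 (62.5%) |
| Saliva days | 48 + 16 = 64 | 58 (90.6%) | 58 − 48 = 10 of 16 (62.5%) |
| Saliva samples | 192 + 64 = 256 | 231 (90.2%) | 231 − 192 = 39 of 64 (60.9%) |

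VC-CBCS need not be complete. With 92/96 (95.8%) in VC-CBCS and 24/32 (75%) in SC, the pooled figure is 116/128 = 90.6%. In general the SC rate at exactly 90% pooled is (0.90 − 0.75 × VC-CBCS rate)/0.25. At a VC-CBCS rate of 95% this is (0.90 − 0.7125)/0.25 = 75%.

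**Effect of counting completers only (13.5).** Suppose all 24 VC-CBCS but only 2 SC participants complete the study. The denominator is 26 × 4 = 104, and more than 90% needs 94. VC-CBCS alone can supply 96, and 96/104 = 92%. If those 26 people answer everything, 13.5 reads 100%. If the six lost SC participants gave only T1 (an assumption), SC capture among all randomized is (2 × 4 + 6 × 1)/32 = 14/32 = 44%, and pooled capture is (96 + 14)/128 = 86%.

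**If post-session forms count as surveys.** Section 13.5 does not say which surveys it covers. With the 14 post-session forms included and everyone in the denominator, VC-CBCS contributes 24 × (4 + 14) = 432 and SC 8 × 4 = 32. Then 432/464 = 93% is reachable with no SC surveys at all.

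**Retention.** More than 80% of 32 needs 26. The matching SC minimum is 2/8 (25%) if VC-CBCS retains 24/24, 4/8 (50%) at 22/24, and 6/8 (75%) at 20/24. Under assumed true retention of 95% in VC-CBCS and 50% in SC, 26 or more of 32 are retained with probability 0.77, while SC reaches 7/8 with probability 0.035.

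**Precision by arm** (two-sided Clopper-Pearson). SC 7/8 = 87.5%, 95% CI 47.3% to 99.7%. VC-CBCS 20/24 = 83.3%, 95% CI 62.6% to 95.3%.

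**The case against.** A reader might infer that the trial could be declared feasible on a pooled 81% retention while SC kept 2 of 8. The documents do not support that reading, for three reasons.

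- SC retention is its own primary outcome (13.3), so 25% would be reported.
- The figures in 23.2 are introduced as anticipated. Section 23.1 rules out hypothesis tests, and nothing makes reaching 80% or 90% a condition for proceeding.
- The >80% names no denominator, so it can be read as applying to 13.3 and 13.4 separately.

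The 2/8 case is also a corner: it needs no losses among 24, which has probability 0.9^24 = 0.08 at an assumed true retention of 90%.

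Other safeguards count too. Reasons for dropout are reviewed in both conditions (12.2, 23.4), and patterns of missing data are examined (12.1, 23.2). Pay for PROs and saliva is equal in the two arms. Section 9 exempts the assessment windows from minimal contact. Phone-delivered surveys and electronic reminders (22) and day-before saliva calls (18) are not limited to VC-CBCS. Fourteen sessions of 90 to 120 minutes could equally cause losses in VC-CBCS.

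Finally, requiring both arms to clear 80% would be a poor rule with 8 SC participants. At an assumed true retention of 85% in both, SC reaches 7/8 with probability 0.66, VC-CBCS reaches 20/24 with probability 0.71, and both do so with probability 0.47, against 0.81 for the pooled figure.

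All of this stands on retention and on how the figures are used. It does not reach data capture. Examining missing-data patterns is a general intention that specifies no table by arm, and 13.5 is still pooled and conditional on completion.

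**Conclusion.** The point holds for data capture. As written, 13.5 and the >90% figure mostly describe VC-CBCS. The >90% can be met with SC PRO capture of 75% when VC-CBCS is at 96%, and with SC capture of about 61% to 63% when VC-CBCS is complete. Outcome 13.5 can look better still, because dropouts are excluded. These are arithmetic limits on what the pooled figures allow, under the planned 24:8 split. They do not predict that SC data will be poor.

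For retention, only a wording gap remains: 23.2 does not say whether >80% refers to each arm or to everyone. A claim that control-arm loss would be hidden, or that a success rule is defective, goes further than the documents allow.

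**What to change.** In 13.5 and 23.2:

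1. Report PRO completeness (T1-T4) and saliva completeness (two collection days) by arm, with all randomized participants in the denominator.
2. Count only assessments scheduled in both arms, and report the VC-CBCS post-session forms separately.
3. Give exact 95% confidence intervals. Present them per time point, or as participants with complete data, because an exact interval over pooled assessments would treat one person's repeated assessments as independent.
4. State that the anticipated >80% is compared with 13.3 and 13.4 separately, and the >90% with each arm separately, as descriptive expectations and not as a pass/fail gate on both arms.

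The cost is a change of wording and a few table rows, using data already being collected. The SC intervals will be wide (7/8 gives about 47% to 100%), one SC participant moves a percentage by 12.5 points, and the SC figures may look less favourable than a pooled one. If the change is made after data have been seen, label it as such.

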### **23.3. Aim 2: Feasibility of intervention delivery**

Technical and logistical issues with VC technology, internet, and software will be recorded. Descriptive methods will summarize the proportion of sessions attended. *We anticipate >75% of VC-CBCS participants will attend >75% of sessions.*

### **23.4 Aim 3: Patient satisfaction and acceptability**

Qualitative data from each exit focus groups will be obtained to help improve the structure and content of the future VC-CBCS and study methods. The Patient Acceptability/Satisfaction survey will be analyzed as an average for the 14 sessions. Items on the group dynamics survey will be evaluated at both time points. Reasons for drop out will be evaluated in both conditions. *We anticipate that patients will find the VC-CBCS highly acceptable and useful, as measured by the Patient Acceptability survey and information provided during the exit focus groups.* If 19 of the 24 VC-CBCS participants find the intervention acceptable (overall score  $\geq 3.5$  out of 5.0), the point and interval estimate will be 79% [95% CI: 61, 100].

### **23.5 Aim 4: Explore changes in patient outcomes, mediators and intervention targets, as well as temporal associations and strength of associations among variables in a preliminary conceptual model, to inform a future efficacy trial**

For each outcome measured before, during and after the intervention, we will obtain estimates of specific mean changes, treatment effects, standard deviations, serial correlations, corresponding confidence intervals indicating levels of precision or standardized effect size estimates (Cohen's *d*) of change. We anticipate that mean changes will favor the VC-CBCS intervention relative to SC.

Various exploratory methods may be used to fully examine the data and generate hypotheses to be evaluated in a future RCT. We may explore the weekly repeated measures for intervention targets and potential mediators/intermediate outcomes to identify targets rated as strongest by patients, and to identify the timing and magnitude of changes in mediators/intermediate outcomes during the VC-CBCS. To better understand potential causal pathways and refine the conceptual model, we may explore temporal correlations among targets, mediators (intermediate/secondary outcomes) and primary patient-reported and clinical outcomes. For example, we may explore associations of mediators with intervention-induced changes in health status, physical and mental symptoms, salivary cortisol, ALT and AST. We will estimate mean  $\log_{10}$  cortisol as a diurnal function of time of day and compute summary values such as the area under the curve (AUC), AUC minus ground, and cortisol awakening.

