## **4 RECRUITMENT**

A two-pronged recruitment strategy will be utilized (primary: in person in liver clinic; secondary: over the phone). Patients will be recruited from the outpatient liver clinics or by phone if referred by a hepatology provider.

For every patient approached for recruitment, a minimal amount of data will be stored in a REDCap Screening Database, separate from the REDCap Research Database. The Screening Log will include: name, MRN, phone number, race, sex, age, and reason for exclusion or not proceeding forward with consent process. Name, MRN and phone number will be deleted after recruitment ends. De-identified race, sex, and age are retained to satisfy CONSORT guidelines for future publications.

Patients will be recruited in 4 waves. Although we seek to enroll/randomize a total of 32 patients with 24 randomized to VC-CBCS and 8 randomized to SC, we will over-consent to accommodate for patients who are deemed ineligible during the screening process or who withdraw consent prior to enrollment. The overall 3:1 randomization scheme allows us to examine feasibility of randomization while allowing us to intensively examine the VC-CBCS group.

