### **12.3 Patient-Reported Outcome Measures (Aim #4)**

To address specific aim #4, several PRO measures will be collected to evaluate primary, secondary and exploratory outcomes to examine the temporal associations and strength of associations among variables in the preliminary conceptual described in Figure 1. PROs will be collected from all participants at four PRO time points (T1-T4). Collection of PRO data serves several preparatory functions for the efficacy trial including making final selection of PROs, contributing to sample size calculations, and exploring preliminary relationships with other variables in the causal pathway.

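### Section 23.5 names Cohen's d with no small-sample correction and no stated SD, in arms of 24 and 8; the bias is small, but Hedges' g removes it at almost no cost.

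*Combined protocol and SAP*

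**What the plan says.** Section 23.5 (Aim 4) promises, for every outcome measured over the course of the intervention, "estimates of specific mean changes, treatment effects, standard deviations, serial correlations", followed by "corresponding confidence intervals indicating levels of precision or standardized effect size estimates". The effect size is given as "standardized effect size estimates (Cohen's *d*) of change". Neither this section nor any other says which SD is the denominator, whether d is computed within each arm or between arms, or whether a small-sample correction applies.

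Section 3.1 has 32 participants "assigned by randomization to VC-CBCS (n=24) or SC (n=8"), and sections 4 and 8 confirm the 3:1 ratio. Section 23.2 anticipates retention above 80%.

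Section 12.3 lists "contributing to sample size calculations" among the purposes of collecting the PRO data, without naming the statistic to be carried forward. Section 23.1 sets the frame: "No hypothesis tests will be conducted", and "Statistical estimates will be reported with 95% confidence intervals (CIs) or standard deviations".

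**The concern.** Dividing a mean difference by a sample SD gives a statistic whose expectation is larger in magnitude than the true standardised effect. The inflation factor depends only on the degrees of freedom of the SD, and it is noticeable when they are few. Here one arm has 8 participants, or perhaps 6 or 7 at the end of the intervention. An analyst who follows section 23.5 literally would compute Cohen's d and would have no instruction to correct it.

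Two things are at stake. First, the published standardised effects would be somewhat too large. If they were computed separately by arm on arm-specific SDs, they would also be too large by different amounts, in a table that readers would compare across arms. Second, required sample size varies as 1/d², so a between-arm d taken forward uncorrected would make the efficacy trial slightly too small.

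**Working it through.** The plan gives no effect size, power or sample-size figure to reproduce, so the check concerns the estimator itself.

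**Inputs from the documents**
- Arms of 24 and 8 (sections 3.1, 4, 8).
- Retention above 80% (section 23.2). At that floor, 0.8 × 24 = 19.2 and 0.8 × 8 = 6.4, so about 19 to 20 in VC-CBCS and 6 to 7 in SC.

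**Assumptions, because the documents give none**
- Normally distributed outcomes.
- A later 1:1 two-arm trial with two-sided alpha 0.05 and 80% power, and a true between-arm d from 0.2 to 0.8.

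**Bias of uncorrected d**

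Expected d divided by true d is 1/J(df), where J(df) = Γ(df/2) / [√(df/2) · Γ((df−1)/2)]. The usual approximation is J ≈ 1 − 3/(4·df − 1).

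| Form of d | n | df | J exact | J approx. | Inflation |
|---|---|---|---|---|---|
| Between arms, pooled SD | 24 + 8 | 30 | 0.975 | 0.975 | +2.6% |
| Within VC-CBCS, own SD | 24 | 23 | 0.967 | 0.967 | +3.4% |
| Within SC, own SD | 8 | 7 | 0.888 | 0.889 | +12.6% |
| Between arms, at retention floor | 20 + 7 / 19 + 6 | 25 / 23 | 0.970 / 0.967 | 0.970 / 0.967 | +3.1% / +3.4% |
| Within VC-CBCS, at retention floor | 20 / 19 | 19 / 18 | 0.960 / 0.958 | 0.960 / 0.958 | +4.2% / +4.4% |
| Within SC, at retention floor | 7 / 6 | 6 / 5 | 0.869 / 0.841 | 0.870 / 0.842 | +15.1% / +18.9% |

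Simulation with a true d of 0.5 agrees for the full-enrolment rows: +2.8%, +3.5% and +12.8%.

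The two within-arm figures need an arm-specific SD. Under normality the sample mean change is independent of the sample SDs, so an arm's own baseline SD gives the same factors as its own change SD. A single SD pooled over both arms gives +2.6% in both. A fixed external SD gives no inflation.

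**Effect on a later trial's size**

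N varies as 1/d², so using 1.026 × d multiplies N by 0.975² = 0.950, about 5% too few. By the normal approximation, n per arm = 2(1.960 + 0.842)²/d² = 15.70/d², rounded up:

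| True d | Expected d | n per arm from true d | n per arm from expected d | Power of the smaller trial |
|---|---|---|---|---|
| 0.2 | 0.205 | 393 | 373 | 78.0% |
| 0.3 | 0.308 | 175 | 166 | 78.0% |
| 0.5 | 0.513 | 63 | 60 | 78.2% |
| 0.8 | 0.821 | 25 | 24 | 79.1% |

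**Sampling error, for scale**

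SE(d) = √(1/24 + 1/8 + d²/64). At d = 0.5 this is √(0.0417 + 0.1250 + 0.0039) = 0.413, so the 95% half-width is 1.96 × 0.413 = 0.81. Over d from 0.2 to 0.8 the half-width is 0.80 to 0.82. The bias of 0.013 at d = 0.5 is 0.013/0.413, about 3% of one SE, and it ranges from 1% to 5% over that span.

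**The case against.** The strongest case against raising this is that it changes almost nothing. The trial is an exploratory, estimation-only pilot, and raw mean changes, treatment effects and SDs are planned alongside any d. In simulation with a true between-arm d of 0.5, d falls below the truth about half the time (49.6%). The middle half of the per-arm sample sizes it implies runs from roughly 25 to 220 with d, and from roughly 26 to 235 with g. The correction does not make the pilot estimate a sound basis for planning. All of this stands, and it sets the grade of the point. What survives is that imprecision is no reason to keep a known error in one direction when one multiplication removes it and slightly reduces the variance as well.

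A reader might also infer four stronger things that the documents do not support.

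- *That the plan prescribes an uncorrected d.* It is silent on correction, and it joins confidence intervals and d by *or*, so d may not be reported for every outcome.
- *That SC effects will be inflated by about 13% against 3% in VC-CBCS.* This needs each arm's change to be divided by that arm's own SD. Within-arm d is a natural reading of an effect size of change, but the plan does not specify it.
- *That the 13% carries into the next trial's sample size.* A two-arm trial would be sized on the between-arm effect, where the figure is 2.6%. Section 12.3 says that PRO data contribute and does not name d.
- *That unequal within-arm bias makes the next trial too small, or flatters VC-CBCS.* Greater inflation in SC tends to shrink the apparent advantage, and the net direction is not fixed. If within-arm values were subtracted, true effects of 0.50 and 0.20 would give 0.517 − 0.225 = 0.292 against a true 0.300. True effects of 0.50 and 0.10 would give 0.517 − 0.113 = 0.404 against 0.400. Because the bias is multiplicative, it is also small in absolute terms if SC changes little.

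**Conclusion.** The point holds as a minor one. Section 23.5 names an estimator that is biased away from zero in small samples and leaves open both the comparison and the SD. The bias is about 2.6% between arms on a pooled SD. On arm-specific SDs, and only then, it is about 12.6% in SC and 3.4% in VC-CBCS, rising to about 15–19% and 4% at the 80% retention floor. If the between-arm d were taken forward, N would be about 5% short and power 1 to 2 points below an assumed 80%.

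These figures rest on normality. The sample-size figures rest also on the assumed alpha, power and allocation of the later trial, and on d being the quantity used, which the plan does not state. The main limit on using these effect sizes for planning is their imprecision, which a CI beside every d would show and the current wording does not require. Label: cheap improvement.

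**What to change.** In section 23.5:

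1. Replace Cohen's d with Hedges' g, that is, d multiplied by the exact gamma-function factor J(df) or by 1 − 3/(4·df − 1).
2. State whether each effect size is within-arm or between-arm, and which SD is its denominator (for example change or baseline, arm-specific or pooled).
3. Change *or* to *and*, so that every effect size carries a 95% CI.
4. If a standardised effect is used in planning the efficacy trial, use the corrected between-arm value together with its interval.

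The cost is a sentence of text and one multiplication in the SAS code, with no new data and no change of design. Reported effect sizes become slightly smaller: multiplied by 0.975 between arms on a pooled SD, or by 0.888 (SC) and 0.967 (VC-CBCS) within arms on their own SDs, at full enrolment.
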